**Table 3. Power estimates based on anticipated outcomes**

Assumption about outcomes among twins	Time to concordant colonization		Power to detect a difference if concordant colonization rate in treated group is 2%
	HR detectable with 90% power	HR detectable with 80% power	
Independent (38 outcomes)	0.35	0.40	0.89
Dependent, 5% twins (40 outcomes)	0.35	0.40	0.87
Dependent, 10% twins (42 outcomes)	0.34	0.39	0.85

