## B. Interim Analyses

Several interim analyses will be performed. We will perform interim analyses for efficacy based on the number of accumulated primary outcomes. Specifically, we will perform an interim analysis after 20 and 30 neonates have been identified to have the primary outcome of concordant colonization. After accruing 20 neonates with the primary outcome, the standard Cox proportional hazards model with main effect of treatment will be fit to estimate the treatment effect, i.e. the hazard ratio comparing the hazard of concordant colonization comparing the intervention and control groups, and the test statistic for the treatment effect will be computed using the methods described in Section

9.C. The DSMB will review the results of the Cox proportional hazards model to determine if the trial will stop for efficacy. The **minimum** criteria for stopping for efficacy will be if the test statistic for the hazard ratio is less than  $Z_r = -2.74$ . If the trial continues, after accruing 30 neonates with the primary outcome, the Cox proportional hazards model will be fitted. The DSMB will review the results of these statistical analyses to determine if the trial will stop for efficacy. The **minimum** criteria for stopping for efficacy will be if the test statistic for the hazard ratio is less than  $Z_r = -2.36$ . If the trial continues, after accruing the 40 neonates with the primary outcome, the treatment effect will be deemed statistically significant if the test statistic for the primary analysis as described below falls within the rejection region defined by  $Z_r = -2.03$ .

To define the above rejection regions, we applied an approximation to the error spending function of O'Brien and Fleming ( $f(t) = \min\{at^3, \alpha\}$ ) such that we spend the overall Type I error rate of 0.05 as 0.0062, 0.0148 and 0.029 after accruing 20, 30 and 40 patients, respectively. The derived rejection regions at each interim analysis (i.e.  $Z_r$ ) are based on the hazard ratio (equivalent to the log-rank test comparing the survival experience in the treatment groups) using an approximation to the information available at each interim analysis (i.e. number of accumulated events at the interim analysis divided by 4).

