The primary analysis will evaluate our hypothesis that detection and treatment of *S. aureus* colonized parents with intranasal mupirocin and topical chlorhexidine gluconate bathing (Treatment Group) will decrease the risk of a child acquiring *S. aureus* with a concordant strain in the NICU within 90 days of randomization relative to the control parents (Control Group). The parent-neonate pair will be the unit of measure. For neonates that do not acquire concordant colonization within 90 days of randomization, their survival time will be computed as the time from randomization to the date of final culture (surveillance or discharge) within 90 days of randomization. We will define the treatment effect as the relative hazard of concordant colonization comparing the Treatment to Control group and will estimate this hazard ratio using the standard Cox proportional hazards model that includes only a main term for treatment. To account for the possibility of clustering within multiple gestation parent/neonate dyads, standard error estimates and bias-corrected and accelerated (BCa) confidence intervals for the log-hazard ratio will be derived using a bootstrap procedure. To preserve the correlation structure within the dyads, the bootstrap procedure will generate 10,000 bootstrap samples by sampling with replacement the parent/neonate dyads, as opposed to resampling the neonates. The analysis described above will be conducted at each pre-planned interim analysis with the test statistic derived from the estimated log hazard ratio from the Cox model and corresponding bootstrap standard error estimate, and the confidence level for the BCa bootstrap confidence intervals will be determined by the rejection region definitions specified in the Interim Analyses section (see Section 9.B).

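### The efficacy boundaries are derived for a log-rank statistic but compared with a Cox estimate over a bootstrap standard error, which costs about 14 points of early-crossing probability at HR 0.4

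*Combined protocol and SAP*

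**What the plan says.** Section 9.B (Interim Analyses) sets efficacy boundaries of -2.74, -2.36 and -2.03 at 20, 30 and 40 primary events. They come from a spending function under which "we spend the overall Type I error rate of 0.05 as 0.0062, 0.0148 and 0.029 after accruing 20, 30 and 40 patients". The derivation rests on a hazard-ratio statistic described as "equivalent to the log-rank test comparing the survival experience in the treatment groups", with information taken as the "number of accumulated events at the interim analysis divided by 4". At the two interim looks, crossing is a minimum criterion for the DSMB. At 40 events, "the treatment effect will be deemed statistically significant if the test statistic for the primary analysis as described below falls within the rejection region". For the computation of the statistic, 9.B refers to 9.C.

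Section 9.C fits a Cox model with treatment only. To allow for multiple births, "the bootstrap procedure will generate 10,000 bootstrap samples by sampling with replacement the parent/neonate dyads". At each look the boundary is compared with "the test statistic derived from the estimated log hazard ratio from the Cox model and corresponding bootstrap standard error estimate". The interval estimates are tied to the same boundaries: "the confidence level for the BCa bootstrap confidence intervals will be determined by the rejection region definitions". Nothing is said about a resample in which one arm has no events.

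Section 9.A states 80% power at HR 0.4, and Table 3 gives 0.35 in its column "HR detectable with 90% power".

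**The concern.** The two sections do not conflict in wording, because 9.B hands the statistic over to 9.C. The problem is calibration. The boundaries spend the stated alpha if the statistic behaves like a log-rank Z. A log hazard ratio over a bootstrap standard error does not behave that way when the treated arm has only a handful of events.

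Two things are at stake. First, if the statistic is conservative, the trial pays for two efficacy looks and gets less from them than designed, and the 80% power is not reached. Second, a resample with no treated event has no finite log hazard ratio. If the software keeps the diverged value, a few such resamples can dominate the standard error. They are most frequent when the treated arm has fewest events, that is, when the result is strongest. Whether a stopping criterion is met would then depend on an unstated software setting. Section 9.C lets methods be finalised before database lock, but both interim looks come before that.

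**Working it through.** **1. The plan's own figures reproduce.**
- Events: 4(1.960 + 0.842)² / (ln 0.4)² = 37.39; with the plan's 2% inflation, 38.1, stated as 38.
- Spending: 0.05t³ at t = 0.5, 0.75 and 1 gives increments of 0.00625, 0.01484 and 0.02891.
- Boundaries: two-sided recursive integration with information 5, 7.5 and 10 gives 2.737, 2.358 and 2.028.

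The boundaries are therefore sound for the statistic they assume.

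**2. An idealised check (singletons, equal arms, equal exposure).** At HR 0.4 each event falls in the treated arm with probability 0.4/1.4 = 0.286, so 5.7 of 20 and 8.6 of 30 are expected. Take 8 treated events of 30, boundary -2.36:
- Score: (8 - 15)/√7.5 = -2.56, crosses.
- Model-based Wald: ln(8/22) / √(1/8 + 1/22) = -1.012/0.413 = -2.45, crosses.
- Bootstrap Wald, non-estimable resamples dropped: -2.30 (SE 1.012/2.30 = 0.440), does not cross.

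At 20 events both the score and bootstrap statistics cross with 3 or fewer treated events. At 30 the cut-off is 8 for the score and 7 for the bootstrap statistic. The binomial probability of crossing at either early look is then 0.50 against 0.35.

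**3. Simulation of the three-look trial.** From the documents: 10% control rate, 5% twin dyads, 90-day limit, 10,000 dyad resamples. Assumed: exponential stay (mean 5.5 weeks, capped at 13), weekly detection, 3 dyads per week, Breslow ties, and either no frailty or a gamma frailty (variance 1) shared within the dyad. There were 1,100 trials per HR 0.4 setting and 700 at HR 0.35.

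| Non-estimable resamples | Kept near -20 | Stopped at -10 | Dropped | Clustered score test |
|---|---|---|---|---|
| Early crossing, HR 0.4 | 0.01 | 0.11 | 0.40 | 0.53 |
| Early crossing, HR 0.4, frailty | 0.02 | 0.08 | 0.33 | 0.48 |
| Early crossing, HR 0.35 | 0.02 | 0.10 | 0.52 | 0.67 |
| Overall rejection, HR 0.4 | 0.71 | 0.74 | 0.75 | 0.79 |
| Overall rejection, HR 0.4, frailty | 0.65 | 0.68 | 0.69 | 0.75 |
| Overall rejection, HR 0.35 | 0.76 | 0.83 | 0.84 | 0.88 |

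Paired gaps at HR 0.4, score minus dropped: early 0.137 ± 0.020 (frailty 0.147 ± 0.021); overall 0.045 ± 0.012 (frailty 0.063 ± 0.014). The model-based Wald statistic crosses early in 0.49. Of the 13.7 early points, 9.5 come from the bootstrap standard error and 13.7 - 9.5 = 4.2 from using Wald rather than score. The median ratio of bootstrap to model SE is 1.09, 1.08 and 1.05 at the three looks.

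**4. Alpha spent under the null (with frailty).**

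| | 20 events | 30 events | 40 events | Total |
|---|---|---|---|---|
| Plan | 0.0062 | 0.0148 | 0.029 | 0.05 |
| Bootstrap Z, dropped (5,000 trials, 1,000 resamples) | 0.0014 | 0.0064 | 0.033 | 0.040 |
| Clustered score (14,668 trials) | 0.0046 | 0.0142 | 0.0325 | 0.051 |

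Early alpha used by the bootstrap Z: (0.0014 + 0.0064)/(0.0062 + 0.0148) = 0.37. For the score test: (0.0046 + 0.0142)/0.0210 = 0.90.

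**5. Resamples with no treated event.** In the idealised case with 20 events, their share is 0.2%, 1.8%, 4.9%, 13% and 37% when 6, 4, 3, 2 and 1 events are in the treated arm. In the simulation at HR 0.4, 95% of first looks have at least one among 10,000.

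Suppose a share p of fits is kept at -20 and the rest have mean b and standard error s. The bootstrap variance is then about p(1 - p)(20 + b)² + (1 - p)s².
- 6 of 20: b = ln(6/14) = -0.85, s = 0.53, p = 0.0022. SE = 1.04, Z = -0.81.
- 4 of 20: b = ln(4/16) = -1.39, s = 0.59, p = 0.0179. SE = 2.54, Z = -0.55.

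The stronger result gets the weaker Z. At 30 events and HR 0.4, the boundary-matched BCa interval excludes 1 while Z fails in 46%, 36% and 8% of trials (kept, stopped at -10, dropped).

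**The case against.** **The bootstrap Wald test is a valid way to handle twins, and it errs on the safe side.** Its total size is 0.040, and a missed crossing only means going on to 40 events. Crossing permits the DSMB to consider stopping but does not oblige it, and the DSMB also sees the BCa interval. Mean events at the first met criterion differ by about two (34.9 dropped, 32.7 score). This stands, and it confines the harm to early stopping and power.

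**In the idealised case the gap is one borderline count.** With 8 treated events of 30 the bootstrap Z misses by 0.06, and that count has probability 0.16. True, but it is a likely count at the design effect, and gaps of similar size appear in the simulations with twins, frailty and varying stay.

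**The levels rest on assumptions.** They do. Separately programmed simulations gave 0.33 to 0.38 against 0.48 to 0.52, and 0.38 against 0.51. Settings with frailty and up to 10% twins gave 0.25 to 0.26 against 0.39 to 0.44. The gap stays at 12 to 18 points throughout.

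**The bootstrap Z is not always conservative.** With resamples dropped and 1 treated event of 20 it is -5.98, against -2.87 for the model-based Wald. That is correct but changes no decision, because the score statistic also crosses there.

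**The score test has drawbacks of its own.** In the same 5,000 null trials its size was 0.056, and another run gave 0.031 on the lower side against about 0.025 nominal. The pooled 0.051, and 0.047 in a further null run, make real inflation unlikely. Test and interval would also no longer come from one procedure. That cost is real and is quantified under the fix.

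**Conclusion.** The concern holds. Compared with boundaries built for a log-rank statistic, the Section 9.C statistic lowers the chance of an early crossing at HR 0.4 by about 14 points (12 to 18 across settings), even when non-estimable resamples are dropped. It lowers overall power by about 5 to 6 points and spends about 37% of the early alpha. The gap is well supported. The absolute levels depend on stay, accrual and twin correlation, which the documents do not give.

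The missing rule for resamples with no treated event is a separate and smaller gap. The choice moves overall power at HR 0.4 by only about 1 to 4 points. It could, however, nearly remove early crossing if the software keeps diverged fits; how far depends on software behaviour that had to be assumed.

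The point should be fixed, but it is not fatal: there is no type I inflation, and the harm falls mainly at the interim looks.

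**What to change.** Before the first look, state in Section 9.C, with a cross-reference from 9.B, that the boundaries at 20, 30 and 40 events are compared with the score (log-rank) statistic from the treatment-only Cox model, with its variance clustered on the family. This statistic matches the derivation of the boundaries, stays finite with no treated events and still allows for twins. Keep the dyad bootstrap for the BCa intervals. State there how resamples with no event in one arm are handled, and report how many occurred.

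The cost is plan wording and minor code. No extra patients are needed and the boundaries and alpha stay as they are. The downside is occasional disagreement between test and interval: at HR 0.4 the score test crossed while the matched BCa interval still included 1 in 11%, 6% and 3% of trials at 20, 30 and 40 events. The reverse did not occur. The DSMB should be told this in advance.

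A single sentence saying that such resamples are dropped would remove the ambiguity but leave the early loss of about 14 points. A change made after an interim look cannot repair that look.

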## **7. Study initiation and baseline data collection**

After results of the pre-randomization screening are completed, a member of the research team will contact the subject(s) to review the results and randomize the positive family units into either treatment or placebo group. After reviewing consent and the study with the parent(s), treatment will commence immediately upon assignment to treatment arm. At that time, the research team will perform the necessary baseline swabs to be sent for culture from the neonate. Neonates' screening cultures will be performed by obtaining a swab from the following anatomical sites: bilateral anterior nares, umbilicus, groin, and peri-anal area. Study team members will also gather residual samples from the clinical laboratory collected during routine clinical care. Parents will be asked about some demographic and medical history information for the researcher to complete on the case report form. Additional information will be obtained from the neonate's medical record (e.g. birth history, maternal prenatal labs).

Those neonates that test positive for *S. aureus* colonization at time of randomization will not be eligible for the primary outcome analysis and they will not contribute to the sample size required to power the primary outcome. Participants will be informed that their child is colonized with *S. aureus*, but participants will be asked to continue the assigned treatment, so secondary outcome data can be collected.

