## **5. Primary and Secondary Endpoints and Outcomes**

### **A. Primary: Primary outcome is neonatal acquisition of *S. aureus* strain that is concordant to parental *S. aureus* strain as determined by periodic surveillance cultures or a culture collected during routine clinical care that grows *S. aureus*.**

Acquisition will be defined as meeting two criteria:

- 1) A neonate who had baseline surveillance cultures that were negative for *S. aureus*
- 2) A neonate who has a subsequent surveillance culture or culture collected during routine clinical care that grows *S. aureus*.

Concordant strains must meet the following criteria:

- 1) Strains that are related using pulsed-field gel electrophoresis (PFGE) analysis, as described below. Isolates will be considered related if their patterns have  $\leq 3$  band differences. Isolates with  $>3$  band differences will be considered epidemiologically different strain types. A neonate who has a subsequent surveillance culture or culture collected during routine clinical care that grows *S. aureus*.
- 2) Alternative typing methods will be used to further discriminate highly prevalent strains or those that are not typable by PFGE.
- 3) The same strain from the initial parent screening is identified from the neonate.

**Primary outcome ascertainment** – We will measure each neonate's baseline *S. aureus* colonization status at the time of study enrollment. As described above, neonates will then have swabs collected weekly after enrollment and at time of discharge from multiple anatomic sites by a study team member. We also will use data from cultures collecting during routine clinical care in the NICU. These cultures include cultures of nasal swabs collected every Tuesday as part of an active *S. aureus* surveillance program and other cultures collected during routine clinical care (e.g. blood cultures, respiratory cultures, wound cultures, etc.). Cultures collected by the study team and cultures collected during routine clinical care will both be used to identify *S. aureus* acquisition in neonates. Of note, nasal surveillance swabs collected as part of the hospital surveillance program are plated on selective media plates to detect *S. aureus* colonization, as previously reported [1].

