**B. Secondary outcomes of interest include:**

**1. Neonatal acquisition of *S. aureus* as determined by periodic surveillance cultures or a culture collected during routine clinical care that grows *S. aureus*.**

Acquisition will be defined as meeting two criteria:

- 1) A neonate who had baseline surveillance cultures that were negative for *S. aureus*
- 2) A neonate who has a subsequent surveillance culture or culture collected during routine clinical care that grows *S. aureus*.

**Outcome ascertainment** – same as for primary outcome

**Observation period or survival time** – same as for primary outcome but does not require the *S. aureus* strain to match that of the parent.

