##### **Plan for Parents Testing Positive for *S. aureus* and disclosure of follow-up results:**

Upon enrollment, all subjects will be provided a brief structured orientation and education session regarding *S. aureus* by a member of the research team. All patient questions will be answered and educational handouts will be provided with references for additional information. Part of the informed consent will include an understanding that parents will be made aware of their *S. aureus* colonization status. If either or both parents are colonized, parents will be informed that one or both parents are colonized,

but we will not share which parent to protect confidentiality. By participating in the trial, others may also become aware that one of both of the parents are colonized simply by their participation in the trial. We will explain that approximately 30% of healthy adults are colonized with *S. aureus*. We do not take special precautions or treat parents differently that are colonized with *S. aureus*. Additionally, we will enroll both parents even if only one parent is colonized, which will aid in protecting the privacy of participants as care providers will not know if a particular parent is colonized simply based on enrollment in the study, as it might be “the other parent” that is colonized.

Once parents are randomized to an assigned treatment, they will continue to be screened for *S. aureus* colonization throughout the study. The results of subsequent testing will not be made available to the parent. Disclosing subsequent testing results may lead to unmasking of the study. Parents will be informed that these results will not be available until the study is complete and the randomization code is un-blinded for data analysis. Parents will be provided with a means to contact the study team to learn their testing results and/or randomization group.

Parents with discordant culture results should not become aware of each other’s colonization status. To decrease or eliminate guilt issues, the study team will not disclose which parent is colonized and will educate parents on the ubiquity of *S. aureus* and emphasize that parents are only one possible source of transmission.

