### **C. Statistical analysis plan**

Final analysis methods and changes in the analyses from those described in the protocol will be documented in the Statistical Analysis Plan prior to locking the database and unmasking the assignment. A CONSORT flow diagram will be created. In addition, descriptive statistics will be calculated to describe the feasibility of the study including number of parent-neonate units approached by a study team member, proportion of parents that consent, proportion of parents colonized among consented, proportion of parents colonized who subsequently do not complete the treatment, and the distribution of adherence, as defined below, to the randomized treatment.

Analyses will be conducted according to the modified intention to treat (mITT) principal. The same day parents are randomized, the neonate will undergo baseline testing to determine baseline *S. aureus* colonization status. Neonates who test positive for *S. aureus* colonization at the time of randomization do not satisfy the inclusion criteria and will not be included in the analysis; hence defining the modified intention to treat analysis. Exploratory analyses of baseline characteristics for the treatment groups will be evaluated by Student t test for continuous data and Pearson's  $\chi^2$  test or Fisher Exact test for categorical data. No missing data should occur for baseline parent and neonate variables. No missing primary or secondary outcomes are expected. However, it is possible that neonates have no subsequent cultures between the baseline culture and NICU discharge, e.g. a neonate enters the study on Friday and is discharged on Sunday prior to their scheduled surveillance culture (Friday in this example) or discharge culture. Based on our definition of observation time (see Sections 5.A and 5.B), such neonates

will contribute no observation time for the analysis of the primary and secondary outcomes. A sensitivity analyses will be conducted where the observation time for these neonates will be defined as the time from randomization to NICU discharge. All tests will be 2-sided with a type-1 error rate set at 0.05. Data will be managed and analyzed using Stata, version 13.0 (Stata Corp., College Station, TX) and R: A language and environment for statistical computing (R Foundation for Statistical Computing, Vienna, Austria, 2014).

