Adverse events, as defined in Section 8, will be reported overall and separately by treatment group. Comparisons across treatment groups will be made using Fisher's Exact tests.

In addition, a series of planned secondary analyses will be conducted including subgroup analyses for the primary outcome, baseline-covariate adjusted analyses for the primary and secondary outcomes, per-protocol (PP) analyses for the primary and secondary outcomes and evaluation of patterns of loss and reacquisition of *S. aureus* among the parents (both treated and control).

Planned subgroup analyses include repeating the analysis for the primary outcome within strata defined by i) neonates with MRSA vs. those with MSSA, ii) collection site of colonization for the parent/caregivers, categorized as nares alone (i.e. all cultured parent/caregivers colonized in the nares) vs. nares + other (i.e. at least one parent/caregiver colonized in the nares) vs. non-nares; iii) LGA (large for gestational age) vs. SGA (small for gestational age); and iv) birthweight (< 1500g vs.  $\geq 1500$ g). The subgroup analyses will be based on Cox proportional hazards models that include a main term for treatment, a main term for subgroup (binary indicator) and the interaction between treatment and subgroup. Confidence intervals and the hypothesis test for no interaction will be derived based on the bootstrap procedure defined above.

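### The MRSA-versus-MSSA subgroup is defined by what the neonate acquires after randomisation, so most neonates have no stratum and the stratum hazard ratios do not compare randomised groups

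*Combined protocol and SAP*

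**What the plan says.** Section 9.C lists four subgroup analyses of the primary outcome. The first is: "Planned subgroup analyses include repeating the analysis for the primary outcome within strata defined by i) neonates with MRSA vs. those with MSSA". The other three use features fixed at baseline: parental colonisation site, size for gestational age and birth weight. All four are to be fitted with Cox models that "include a main term for treatment, a main term for subgroup (binary indicator) and the interaction between treatment and subgroup".

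The analysed population starts free of *S. aureus*. Section 4.C.7 says "Those neonates that test positive for *S. aureus* colonization at time of randomization will not be eligible for the primary outcome analysis", and Section 9.C repeats this for the mITT population: "Neonates who test positive for *S. aureus* colonization at the time of randomization do not satisfy the inclusion criteria and will not be included". Section 5.A makes negative baseline cultures part of the definition of acquisition.

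The primary event is concordant acquisition, for which Section 5.A requires: "The same strain from the initial parent screening is identified from the neonate". Discordant acquisition is also foreseen. The any-strain secondary outcome in Section 5.B "does not require the *S. aureus* strain to match that of the parent", and Section 6.D tells families that "parents are only one possible source of transmission". In the primary analysis, neonates without concordant acquisition stay in the risk set and are censored at their last culture within 90 days.

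**The concern.** No analysed neonate has MRSA or MSSA at randomisation. The label can come only from a later positive culture, which is either the primary event or a discordant acquisition. Two problems follow.

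- **No stratum for most neonates.** The model needs a subgroup value for each neonate it includes, and the plan does not say what to do with those who acquire nothing.
- **Selection on the outcome.** If treatment works, fewer treated neonates acquire a concordant strain, so entry to a stratum depends on the arm. The stratum HR then compares selected neonates, not randomised groups.

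Section 9.C recognises this hazard elsewhere. It warns that conditioning on compliance, a post-randomisation variable, may bias the comparison, and it adds an inverse-probability-weighted analysis. The strain subgroup is tied more closely to the outcome and has neither a warning nor a remedy.

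At stake are the HRs reported for each strain type. A real benefit could look smaller, absent, reversed or larger in a stratum, or a false MRSA/MSSA difference could appear.

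**Working it through.** **The plan's own figure.** Section 9.A asks for 38 events for HR 0.40, 80% power and two-sided 5%, including about 2% for interim looks. Schoenfeld's formula gives 4 × (1.960 + 0.842)² / (ln 0.40)² = 37.4, and 37.4 × 1.02 = 38.1, so the figure is reproduced. The plan gives no figure for the strain subgroup.

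**Inputs.** From Section 9.A: 90-day control concordant risk 10% (the plan gives the 10%; I apply it at 90 days) and HR 0.40, so the treated risk is 1 − 0.90^0.40 = 4.1%. Assumed, because the documents give no values: discordant risk *d* of 0 to 20%, discordant HR of 0.25 to 1.5, MRSA share 20% (also 50% in the trial-size runs), exponential times, and no clustering.

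**Who has a stratum.** With 90-day follow-up and discordant acquisition independent of arm, the chance of acquiring nothing is 0.90 × (1 − *d*) in control and 0.9587 × (1 − *d*) in treatment.

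| *d* | No stratum, overall | With a stratum, control | With a stratum, treated |
|---|---|---|---|
| 0% | 92.9% | 10.0% | 4.1% |
| 5% | 88.3% | 14.5% | 8.9% |
| 10% | 83.6% | 19.0% | 13.7% |
| 20% | 74.3% | 28.0% | 23.3% |

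Entry to a stratum differs by arm in every row.

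**Option 1: only acquirers are analysed.** With *d* = 0, every neonate in a stratum has the event, so the model compares only timing among cases and the HR goes to about 1. Large-sample simulation (300,000 to 400,000 neonates per arm, true HR 0.40 for both strain types, several follow-up patterns) gives:

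| Discordant rate | Discordant HR | Stratum HR |
|---|---|---|
| 5% | 1.0 | 0.54–0.60 |
| 10% | 1.0 | 0.47–0.51 |
| 20% | 1.0 | 0.43–0.45 |
| 10% | 0.7 | 0.62–0.69 |
| 10% | 0.4 | 0.93–0.99 |
| 10% | 0.25 | 1.23–1.34 |
| 10% | 1.5 | 0.35–0.37 |

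If follow-up instead stops at discordant acquisition, the first three rows become 0.64–0.66, 0.55–0.59 and 0.47–0.49. The interaction is distorted less: a true ratio of HRs of 0.40 (MRSA 0.20, MSSA 0.50) becomes 0.42–0.61.

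**Option 2: non-acquirers are placed with MSSA.** The MSSA HR stays at 0.39–0.41, and the MRSA HR is distorted as in option 1. With no true interaction and *d* = 10%, the MRSA/MSSA ratio of HRs is about 1.3, 1.7, 2.3, 3.3 and 0.9 for discordant HRs of 1.0, 0.7, 0.4, 0.25 and 1.5.

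**At trial size.** Forty events need 2 × 40 / (0.10 + 0.0413) = 566 neonates. The runs used 286 per arm, which gives 286 × 0.1413 = 40.4 events, with 1,500 trials per setting and a common true HR of 0.40. A Wald interaction test at 1.96 was false-positive in:

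- 4–6% of trials under option 1;
- 4–7% under option 2 if discordant acquisition is unaffected, 22–25% at discordant HR 0.4 and 32–43% at 0.25.

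**The alternatives.** Cause-specific analysis with all neonates at risk returns 0.39–0.41 for discordant HRs of 0.4 to 1.5. A subgroup based on parental isolates creates no false interaction (ratio 0.98–1.03 when the truth is 1).

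**The case against.** **The model can be read another way.** Each neonate can be given one row per strain type, as in the Lunn–McNeil competing-risks form. The model is then exactly treatment, a binary type indicator and their interaction, with everyone at risk for both types. A run with a true ratio of 0.40 returned 0.38–0.41. This is right, and it shows that a sound analysis fits the stated model form. But the plan does not describe it, and its words stratify neonates, so it is a remedy and not a defence of the text.

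**The list is shorthand.** Large versus small for gestational age also leaves neonates out, and Section 9.C says final methods will be documented before lock. Leaving infants out on a baseline feature keeps the comparison randomised; leaving them out on the outcome does not. The pre-lock documentation is the right place for the correction.

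**The worst figures need strong assumptions.** A discordant HR of 0.25 means treatment works better on non-parental strains than on the parental strains it targets. Nothing in the documents supports that value. Some effect is possible: a strain that a parent picks up after screening counts as discordant, and the plan itself studies parental reacquisition. Results above 1 should still be read as an extreme. With no effect on discordant acquisition, the range is 0.43–0.60 for discordant rates of 5–20%.

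**The 4–6% false-positive rate assumes equal MRSA shares.** This stands. With MRSA shares of 40% among concordant and 10% among discordant strains (*d* = 10%, discordant HR 1), the stratum HRs are about 0.63 and 0.46 and the false-positive rate is about 9%. With the shares reversed (10% and 40%), they are about 0.40 and 0.53, with a rate of about 1%.

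**The stakes are limited.** This also stands: it is one secondary subgroup analysis with no role in stopping or in the primary conclusion.

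**Conclusion.** The concern holds. As written, the subgroup is set after randomisation, largely by the outcome, and the plan has no rule for the roughly 74–93% of neonates who acquire nothing. Dropping them leaves neither stratum HR a randomised comparison; placing them with MSSA leaves the MRSA HR invalid. These conclusions follow from the text and need no assumed rate.

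The direction and size of the error do depend on assumptions: where non-acquirers are placed, how common discordant acquisition is, whether treatment alters it, and the MRSA share of each kind of strain. The bias shrinks as discordant acquisition rises if treatment does not affect it. The primary analysis is untouched.

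**What to change.** Before database lock and unmasking, replace the definition of subgroup (i) with one of these:

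- **Cause-specific events.** Analyse MRSA-concordant and MSSA-concordant acquisition as separate event types, with all mITT neonates at risk for both. The duplicated-row form keeps the planned interaction term and the family-level bootstrap. This stays closest to the question of neonatal strain type.
- **Parental baseline isolates.** Define strata as any MRSA versus MSSA only among the parents' screening isolates. Each randomised family has a positive parent (Section 4.C.6), and isolates are tested for MRSA/MSSA (Section 7.B). This asks about parental carriage instead. Two caregivers may be enrolled, so some families will carry both types; report them separately or exclude them in a sensitivity analysis. If 10, 25 or 50% of any-MRSA families are mixed, a true ratio of 0.40 is diluted to 0.43–0.45, 0.49–0.53 or 0.55–0.61.

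The cost is SAP wording, which Section 9.C allows before lock. Section 7.B says parental MRSA/MSSA testing is not done in real time and that MRSA-colonised parents will not be identified. For the second option, the SAP should confirm that the results will be complete and available for analysis.

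State in advance that the strain comparison is imprecise. With 40 events and an assumed 10–50% MRSA share (4–20 events), power for a ratio of 0.40 is about 10–30%. For example, at 20% the variance is 4/8 + 4/32 = 0.625, which gives about 21% power and a 95% interval that multiplies and divides the ratio by 4.7. Allowing for unequal events by arm, these become 15% and 7.4.

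In the same edit, make the three parental-site categories of subgroup (ii) mutually exclusive and test them with 2 degrees of freedom. A family in which every caregiver is nasally colonised now meets two of the definitions, and three levels do not fit one binary indicator.
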